6. STUDY INTERVENTION AND CONCOMITANT THERAPY

Study intervention is defined as any investigational intervention(s)/product(s) (IP), marketed product(s), placebo, or medical device(s) intended to be administered to a study participant according to the study protocol.

Study intervention will only be administered in the clinic; hence Visit 2 (Week 0) and Visit 10 (Week 26) are required to be in-clinic visits.

6.1. Study Intervention Administered

GSK3511294 is a humanised IgG antibody (IgG1, kappa) with human heavy and light chain frameworks. GSK3511294 liquid drug product will be supplied by GSK in a Type I glass syringe (with a 1/2-inch, 29-gauge thin wall, staked needle and sealed with a latex-free rubber plunger). The drug product and syringe will be assembled in a single use, disposable safety syringe to enable delivery of the drug product. Each device enables SC delivery of 100 mg GSK3511294 in 1.0 mL sterile liquid formulation. The formulation contains L-histidine, trehalose dihydrate, L-arginine hydrochloride, disodium edetate (EDTA), water for injection and polysorbate 80.

The placebo in this study will be 0.9% sodium chloride solution contained in a PFS also supplied by GSK.

An overview of study intervention is provided in [Table 2](#).

Table 2 Overview of Study Intervention

ARM Name	GSK3511294 100 mg	Placebo
Intervention Name	GSK3511294 100 mg SC	Placebo
Type	Biologic	N/A
Dose Formulation	Sterile liquid formulation in single-use PFS	Sterile 0.9% (w/v) sodium chloride solution in single-use PFS
Unit Dose Strength(s)	100 mg/mL; 1.0 mL (deliverable)	N/A, 1.0 mL (deliverable)
Dosage Level(s)	100 mg once every 26 weeks (Week 0 and Week 26)	Placebo once every 26 weeks (Week 0 and Week 26)
Route of Administration	SC injection	SC injection
Use	Experimental	Placebo
IMP and NIMP	IMP	IMP
Sourcing	Provided centrally by the Sponsor	Provided centrally by the Sponsor
Packaging and Labelling	Study Intervention will be provided in PFS. Each PFS will be labelled as required per country requirement.	Study Intervention will be provided in PFS. Each PFS will be labelled as required per country requirement.

PFS=Pre-filled safety syringe, IMP=Investigational Medicinal Product, N/A=not applicable

6.1.1. Medical Devices

The GSK manufactured medical devices (or devices manufactured for GSK by a third party) provided for use in this study are injection devices:

- A pre-filled syringe contained within a safety syringe. The devices used in the study are representative of the devices planned to be marketed for the product.
- The components that comprise the pre-filled syringe (glass barrel with pre-staked needle and plunger) are sourced from Becton Dickinson. The pre-filled syringe is filled with study intervention (GSK3511294 or placebo) and assembled at GSK, Barnard Castle.
- The safety syringe components are manufactured by Becton Dickinson. The safety syringe components are assembled with the pre-filled syringe at GSK, Barnard Castle.

The Instruction for use (IFU) of the injection device will be provided. The instructions were developed and optimised as a result of formative human factors studies for mepolizumab and are representative of those that are planned for GSK3511294.

All device deficiencies, (including malfunction, use error and inadequate labelling) shall be documented, and reported by the investigator throughout the clinical investigation (see Section 8.4.8) and appropriately managed by GSK.

6.2. Packaging and Labelling

The contents of the label will be in accordance with all applicable regulatory requirements.

6.3. Preparation/Handling/Storage/Accountability

- The investigator or designee must confirm appropriate temperature conditions have been maintained during transit for all study intervention received and any discrepancies are reported and resolved before use of the study intervention.
- Only participants enrolled in the study may receive study intervention and only authorised site staff may supply or administer study intervention.
- All study interventions must be stored in a secure, environmentally controlled, and monitored (manual or automated) area in accordance with the labelled storage conditions with access limited to the investigator and authorised site staff.
- The investigator, institution, or the head of the medical institution (where applicable) is responsible for study intervention accountability, reconciliation, and record maintenance (i.e., receipt, reconciliation, and final disposition records).
- Further guidance and information for the final disposition of unused study intervention are provided in the SRM.
- Under normal conditions of handling and administration, study intervention is not expected to pose significant safety risks to site staff. Take adequate precautions to avoid direct eye or skin contact and the generation of aerosols or mists. In the case of unintentional occupational exposure notify the monitor, Medical Monitor and/or GSK study contact.

- A Material Safety Data Sheet (MSDS)/equivalent document describing occupational hazards and recommended handling precautions either will be provided to the investigator, where this is required by local laws, or is available upon request from GSK.

6.4. Measures to Minimise Bias: Randomisation and Blinding

6.4.1. Treatment Assignment

- Eligible participants will be centrally randomised using an IRT system.
- The randomisation schedule will be generated using the GSK validated randomisation software RandAll NG. Separate randomisation schedules will be created for each country. Participants will be assigned to study intervention in accordance with the randomisation schedule. Once a randomisation number has been assigned to a participant, it cannot be reassigned to any other participant in the study.
- Randomisation will be stratified according to the participant's baseline ICS dose (aiming to up to 50% approximately of participants on medium ICS dose; see [Appendix 10](#)).
- At Visit 2 (Week 0), those participants who meet the randomisation criteria will be randomised in a 2:1 ratio to receive one of the following study treatments in addition to their stable maintenance asthma treatment:
 - GSK3511294 100 mg SC
 - Placebo SC
- Study intervention will be administered in the clinic at Visit 2 (Week 0) and Visit 10 (Week 26) as per the SoA (Section [1.3](#)).

6.4.2. Blinding

- The IRT system will be programmed with blind-breaking instructions. In case of an emergency, the investigator has the sole responsibility for determining if unblinding of a participant's intervention assignment is warranted. Participant safety must always be the first consideration in making such a determination. If the investigator decides that unblinding is warranted, the investigator should make every effort to contact GSK prior to unblinding a participant's intervention assignment unless this could delay emergency intervention of the participant. If a participant's intervention assignment is unblinded, GSK must be notified within 24 hours after breaking the blind. The date and reason that the blind was broken must be recorded in the source documentation and case report form (CRF), as applicable.
- Investigators will remain blinded to each participant's assigned study intervention throughout the course of the study. To maintain this blind, GSK3511294 and placebo will be administered from PFSs that will be identical in appearance.
- If a participant's intervention code is unblinded by the investigator or treating physician, that participant will continue with all study visits but will not receive the

second dose of study intervention at Week 26. The primary reason for the event or condition which led to the unblinding will be recorded in the CRF (see Section 7.1).

- To maintain the blind, haematology data (absolute and % values of eosinophils, lymphocytes, basophils, neutrophils, and monocytes) from post-randomisation samples will not be reported to the site or the central study team.
- GSK's Global Clinical Safety and Pharmacovigilance (GCSP) staff may unblind the intervention assignment for any participant with an SAE. If the SAE requires that an expedited regulatory report be sent to one or more regulatory agencies, a copy of the report, identifying the participant's intervention assignment, may be sent to investigators in accordance with local regulations and/or GSK policy.

6.4.3. Controlled Early Access to Unblinded PK and PKPD Data

Designated independent representative(s) may be unblinded for performing population PK and PKPD dataset preparation and draft PK and PKPD model development using scrambled (random reassignment of subject identification numbers) PK and PKPD unblinded datasets, including baseline demographic characteristics. No adverse event data or efficacy data will be included.

6.5. Study Intervention Compliance

Both doses of GSK3511294 or placebo will be administered under medical supervision via SC injection to participants by the investigator or designee at the study site. Dose administration details (date and time) will be recorded in the source documents and reported in the CRF.

Participants will be monitored in clinic for a minimum of 2 hours post-dose to monitor for immediate hypersensitivity and any other untoward effects. In the event of an acute severe reaction (e.g., anaphylaxis) following administration of GSK3511294, there are personnel/staff onsite at the treatment facility who are appropriately trained in basic life support to manage the participant including administration of medications (e.g., epinephrine), and have access to a system that can promptly transport the participant to another facility for additional care if appropriate.

6.6. Dose Modification

Dose modification is not allowed.

6.7. Continued Access to Study Intervention after the End of the Study

The investigator is responsible for ensuring that consideration has been given to the post-study care of the participant's medical condition whether or not GSK is providing specific post-study treatment.

At the end of the study, participants will be eligible to screen to enter the OLE Study 212895 and have continued access to open-label GSK3511294 if he/she:

- has received both doses of study intervention (at Week 0 and Week 26), AND
- completed the scheduled Exit Visit at Week 52, AND
- did not meet any of the study intervention discontinuation conditions (Section 7.1) during the study.

For participants who enrol into the 12-month OLE study, the Day 1 visit of the OLE study can occur on the same day as the Exit Visit of the current study. Specific details on the OLE study will be documented separately.

Participants who do not enter the OLE study will complete a follow-up visit/call and be prescribed alternative asthma therapy if needed and as determined by the study investigator.

6.8. Treatment of Overdose

The dose of GSK3511294 that is considered to be an overdose has not been defined. There are no known antidotes and there is no specific treatment for a suspected overdose. In FTIH study 205722 (refer to the current IB [GlaxoSmithKline Document Number [2016N295843_03](#) or later]), single SC doses of GSK3511294 up to 300 mg were well tolerated by adult participants with mild/moderate asthma (6 participants received a 300 mg SC dose).

Each PFS will enable the delivery of a single dose of study intervention (see Section 6.1). In the event of an overdose, the investigator should:

- Contact the Medical Monitor immediately.
- Treat the participant with active supportive care as dictated by the participant's clinical status in the knowledge of the long half-life (approximately 41 days) of GSK3511294.
- Closely monitor the participant for AE/SAE and laboratory abnormalities for 30 weeks following the last administered dose.
- Document the quantity of the excess dose as well as the duration of the overdosing in the CRF.

Decisions regarding discontinuation or delay of another dose of study intervention will be made by the investigator in consultation with the Medical Monitor based on the clinical evaluation of the participant.

6.9. Concomitant Therapy

At pre-screening and/or screening, information on the participant's baseline maintenance asthma therapy will be collected and recorded in the eCRF.

Any medication or vaccine (including over-the-counter or prescription medicines, vitamins, and/or herbal supplements) that the participant is receiving at the time of enrolment or receives during the study must be recorded in the eCRF along with:

- reason for use
- dates of administration including start and end dates
- dosage information including dose and frequency (any dose changes are to be recorded for OCS)

The Medical Monitor should be contacted if there are any questions regarding concomitant or prior therapy.

6.9.1. Permitted Medications and Non-Drug Therapies

Throughout the study, participants are to be maintained on their baseline maintenance asthma treatment consisting of ICS plus at least one other controller, e.g. LABA, LAMA, with or without maintenance OCS (see inclusion criteria 4 and 5, Section 5.1). It is recognised that in a year-long study, changes may need to be individualised if clinically crucial for a participant. The investigator is encouraged to discuss any cases with the Medical Monitor before initiating changes to a participant's maintenance asthma medication.

Additional asthma medications such as theophyllines and anti-leukotrienes will be permitted as maintenance provided that they have been taken regularly in the 3 months prior to screening (Visit 1). If uncertain whether a medication is permitted, please confirm with the Medical Monitor.

Albuterol/salbutamol is permitted throughout the study but should be withheld in the 6-hour period prior to spirometry assessments, if possible. Study-provided albuterol/salbutamol should not be recorded in the eCRF, only in the eDiary.

LABAs, LAMAs, and fixed dose combinations of ICS/LABA or ICS/LABA/LAMA should be withheld for ≥ 12 hours prior to spirometry, if possible.

Continuous Positive Airway Pressure (CPAP) or Bilevel Positive Airway Pressure (BiPAP) for the treatment of obstructive sleep apnoea is permitted, if initiated prior to the Screening Visit (Visit 1). This treatment must be captured in the eCRF.

Allergen-specific immunotherapy is permitted provided that it has been taken regularly in the 6 months prior to screening (Visit 1).

Participants can be vaccinated against SARS-CoV-2 infection using authorized COVID-19 vaccines in line with local/national guidelines for COVID-19 vaccines. Experimental COVID-19 vaccines are not permitted.

COVID-19 vaccine administration and the administration of the study intervention should be separated by 14 days if possible, in order to be able to properly assess study injection site/treatment reactions.

Participants can be treated for SARS-CoV-2 infection using authorized COVID-19 treatments (including monoclonal antibodies) in line with local/national guidelines. Experimental COVID-19 treatments are not permitted.

6.9.2. Prohibited Medications and Non-Drug Therapies

The following medications are not allowed prior to screening (Visit 1), according to the following schedule, or during the study:

Medication	Washout Time Prior to Screening Visit
Investigational drugs	1 month or 5 half-lives whichever is longer
Omalizumab [Xolair], dupilumab [Dupixent]	130 days
Mepolizumab [Nucala™], reslizumab [Cinqair/Cinquaero], benralizumab [Fasenra]	12 months
Other monoclonal antibodies	5 half-lives
Experimental anti-inflammatory drugs (non biologicals)	3 months

Immunosuppressive medications such as those listed below (not all inclusive)
Corticosteroids if used to treat a condition other than asthma 
 • Intramuscular, long-acting depot • Regular systemic (oral or parenteral)
Methotrexate, cyclosporin, azathioprine
Oral gold
Chemotherapy used for conditions other than asthma

Additionally, Bronchial Thermoplasty and Radiotherapy are excluded for 12 months prior to Visit 1 and throughout the study. CPAP, BiPAP, and oxygen therapy should not be initiated during the run-in period.

6.9.3. Rescue Medicine

Trade label albuterol/salbutamol metered dose inhalers (MDIs) will be provided as rescue medication throughout the study. Albuterol/salbutamol will be sourced for all centres. Use of low dose ICS-formoterol as rescue medication is not allowed during the study.

Participants will be dispensed an MDI at Screening Visit 1 to be used primarily to treat asthma symptoms on an as needed basis and also during the reversibility assessments (see Section 8.2.3.1). The MDI should be replaced as needed.

Although the use of rescue medications is allowable (at any time during the study), the use of rescue medications should be withheld, if possible, for at least 6 hours prior to the spirometry assessments. Rescue medication usage will be recorded in the eDiary.

7. DISCONTINUATION OF STUDY INTERVENTION AND PARTICIPANT DISCONTINUATION/WITHDRAWAL

7.1. Discontinuation of Study Intervention

No further doses of study intervention will be administered to participants who meet any of the following permanent treatment discontinuation conditions at any time during the study treatment period:

- Liver Chemistry: Meets any of the protocol-defined liver chemistry stopping criteria (see Section 7.1.1)
- ECG: Meets any of the protocol-defined QTc stopping criteria (see Section 7.1.2)
- Pregnancy: Positive pregnancy test (see Section 8.4.5)
- Severe allergic reaction/anaphylaxis: Participants with severe allergic reaction/anaphylaxis with no clear alternative cause (see Appendix 8)
- Vasculitis: Participants with confirmed vasculitis or suspected vasculitis with no alternative explanation (see Section 7.5).
- Study treatment unblinded: Unblinding of the study treatment assigned to a participant (see Section 6.4.2).

If a participant meets any of the treatment discontinuation conditions or chooses (for any reason) not to receive another dose of study intervention before the end of the protocol specified randomised intervention period:

- The investigator will make every effort to encourage the participant to remain in the study **and** to continue with all remaining study visits, including the Exit and Follow-up Visits.
- The primary reason for discontinuation of study intervention (e.g., AE, lack of efficacy, protocol deviation, investigator discretion, consent withdrawn etc.) must be recorded in the eCRF.
- Participants will be provided with the option to continue their scheduled visits in-clinic, at home, or by phone. The required study assessments will depend on whether the participant is attending the visit in-clinic, at home, or by phone. At a minimum, an assessment of exacerbations, AEs, SAEs, and concomitant medications will be completed.
- If for any reason, the participant later chooses to withdraw from the study, a Withdraw from Study Visit (see Section 7.2) should be conducted according to the SoA (Section 1.3).

[figure not shown]
7.1.1. Liver Chemistry Stopping Criteria

Liver chemistry stopping criteria, and increased monitoring criteria have been designed to assure participant safety and evaluate liver event aetiology.

Discontinuation of study intervention for abnormal liver tests is required when:

- a participant meets one of the conditions outlined in the algorithm or
- in the presence of abnormal liver chemistry not meeting protocol-specified stopping rules, the investigator believes that it is in the best interest of the participant.

[figure not shown]
Liver Chemistry Stopping Criteria Algorithm

Abbreviations: ALT = alanine transaminase; INR = international normalised ratio; SAE = serious adverse event; ULN = upper limit of normal, Tbili = Total bilirubin

Refer to [Appendix 6](#) for required Liver Safety Actions, Monitoring, and Follow-up Assessments.

Liver Chemistry Increased Monitoring Algorithm with Continued Study Intervention for Participants with ALT ≥3xULN but <8xULN and do not meet any of the liver stopping criteria

Abbreviations: ALT = alanine transaminase; Tbili = total bilirubin; INR = international normalised ratio; SAE = serious adverse event; ULN = upper limit of normal, Tbili = Total bilirubin.

Refer to [Appendix 6](#) for required Liver Safety Actions, Monitoring and Follow-up Assessments.

7.1.1.1. Study Intervention Restart or Rechallenge after liver stopping criteria met

Study intervention restart or rechallenge after liver chemistry stopping criteria are met by a participant in this study will not be permitted.

7.1.2. QTc Stopping Criteria

Details on performing ECG assessments can be found in [Section 8.3.3](#).

The QT interval corrected using Fridericia’s formula (QTcF) must be used for *each individual participant* to determine eligibility for and discontinuation from the study intervention. This formula may not be changed or substituted once the participant has been enrolled.

For this study, the following QTc stopping criteria will apply:

- QTcF >500 msec OR uncorrected QT >600 msec
- Change from baseline of QTcF >60 msec

For participants with underlying bundle branch block, follow the discontinuation criteria listed below:

Baseline QTcF with Bundle Branch Block	Discontinuation QTcF with Bundle Branch Block
<450 msec	>500 msec
450 – 480 msec	≥530 msec

The QTcF value from the 12-lead ECG central over-read at randomisation Visit 2 should be used as baseline QTcF value for any changes from baseline calculations during the study. After randomisation 12-lead ECG central over-read values should be used to assess QTc stopping criteria, with the exception of Visit 10 (Week 26) where 12-lead ECG machine read values should be used.

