Physical Examination		X																	X	X	Include height and weight for the complete physical exam at Screening Visit 1. Height can be omitted for subsequent visits.	
Vital Signs		X	X			X			X		X	X			X			X	X	X		
12-lead ECG		X	X	X							X	X							X	X	ECG must be performed and assessed pre-dose. Twelve-lead ECG central over-read values should be used at all visits with the exception of Visit 2 and Visit 10 where 12-lead ECG machine read values should be used.	

Protocol Activity	Pre-Screening	Screening/Run-in	Intervention Period and Exit Visit (visit window is ±7 days)																	Follow-up/Withdrawal (±7 days)		Notes
			Visit	V0 ^a	Visit 1 ^a	V2 ^b R*	V3	V4	V5	V6	V7	V8	V9	V10	V11	V12	V13	V14	V15	V16	Exit V17	
Study Week	-8 to -6	-6 to -1	0	2	4	8	12	16	20	24	26	28	32	36	40	44	48	52	26 or 52	56	R* =Randomisation WS=Withdraw from study visit (see footnote c) FU=Follow-up visit/call (only required for participants not entering OLE study)	
Study Day	-56 to -42	-42 to -7	1	14	28	56	84	112	140	168	182	196	224	252	280	308	336	364		392		
AE/SAE Assessment	X ^g	X ^g	X	X	X	X	X	X	X	X	X	X	X	X	X	X	X	X	X	X	X	AE=Adverse events; SAE=Serious adverse events; see footnote g.
Laboratory Assessments																						
Haematology with white blood cell count ^f		X ^e	X	X	X	X	X		X		X	X	X		X		X	X	X			For dosing days (Week 0 and Week 26), obtain sample prior to dosing; see footnotes e and f.
Total IgE			X																			
Clinical Chemistry		X	X		X	X	X		X		X	X		X		X	X	X	X			Include liver chemistry.
Pregnancy Test (WOCBP only)		X	X		X	X	X	X	X	X	X		X	X	X	X	X	X	X	X	X	Serum pregnancy test should be done at screening Visit 1 and Exit Visit/Withdraw from study visit; urine pregnancy tests should be done for all other assessments; WOCBP=Women of childbearing potential; See Section 8.3.5 for additional information.
Urinalysis		X	(X)															X	X			Conduct at Visit 2 if not completed at Visit 1. Note: dipstick, send for analysis if abnormality is identified by dipstick.
Anti-MPO antibody, anti-PR3 antibody, ANA, and anti-dsDNA antibody			X																			ANA=antinuclear antibodies; MPO=myeloperoxidase; PR3=proteinase 3. Collected baseline sample will be stored and may be tested if necessary (see Section 7.5).
Complement C3 and C4			X				X				X				X			X	X			
PK sample			X	X	X	X	X		X		X	X	X		X			X	X			For dosing days (Week 0 and Week 26), obtain sample prior to dosing.

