5.3.2. Randomisation Exclusion Criteria**RANDOMISATION EXCLUSION CRITERIA**

1. **Laboratory abnormality:** Evidence of clinically significant abnormality in the haematological, biochemical or urinalysis screen at Visit 1, as judged by the investigator.
2. **Liver chemistry test:** Participants who meet the following based on results from sample taken at Screening Visit 1:
 - a) Alanine aminotransferase (ALT) >2x upper limit of normal (ULN)
 - b) Total bilirubin >1.5x ULN (isolated bilirubin >1.5xULN is acceptable if bilirubin is fractionated and direct bilirubin <35%)
 - c) Cirrhosis or current unstable liver or biliary disease per investigator assessment defined by the presence of ascites, encephalopathy, coagulopathy, hypoalbuminaemia, oesophageal or gastric varices, or persistent jaundice.

NOTES: Stable non-cirrhotic chronic liver disease (including Gilbert's syndrome, asymptomatic gallstones, and chronic stable hepatitis B or C) is acceptable if the participant otherwise meets entry criteria.

3. **ECG:** QTcF \geq 450msec, or QTcF \geq 480 msec for participants with Bundle Branch Block, in the 12-lead ECG machine read at randomisation Visit 2 are excluded. Participants are excluded if an abnormal ECG finding from central over-read of the 12-lead ECG conducted at Screening Visit 1 is considered to be clinically significant and would impact the participant's participation during the study, based on the evaluation of the Investigator.
4. **Unstable Asthma:** Participants with a clinically significant asthma exacerbation in the 7 days prior to randomisation should have their randomisation visit delayed until the investigator considers the participant's asthma to be stable (see Section 5.6).
5. **Maintenance Asthma Therapy:** Any changes in the dose or regimen of baseline ICS and/or additional controller medication (except for treatment of an exacerbation) during the run-in period.

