4.1.2. Baseline Definition

Baseline values for visit based assessments and eDiary assessments are defined in Table 3.

Unless otherwise stated, if baseline is missing, no derivation will be performed and baseline will be set to missing.

Parameter	Study Assessments Collected Prior to Dosing		Baseline Definition	
	Screening (Visit 1)	Day 1 Pre-Dose (Visit 2)		
Efficacy, Health Outcom	nes and Other			
SGRQ total and domain		Х	Day 1 pre-dose	
scores				
ACQ-5		Х	Day 1 pre-dose	
Pre-bronchodilator FEV ₁	Х	X	Day 1 pre-dose	
Post-bronchodilator FEV ₁	Х	X	Day 1 pre-dose	
PROMIS Fatigue items score		X	Day 1 pre-dose	
ADSD/ANSD weekly mean score	X (daily following Screening)		Average of measurements from Day -7 to Day -1 inclusive (at least 4 days must be non-missing)	
Awakenings at night due to asthma symptoms requiring rescue medication use 2-week mean	X (daily followin	g Screening)	Average of measurements from Day -7 to Day -1 inclusive (at least 4 days must be non-missing)	
Morning PEF 2-week mean	X (daily followin	g Screening)	Average of measurements from Day -6 to Day 1(pre-dose) inclusive (at least 4 days must be non-missing)	
Daily asthma symptom scores 2-week mean	X (daily followin	g Screening)	Average of measurements from Day -6 to Day 1(pre-dose) inclusive (at least 4 days must be non-missing)	
Mean number of occasions of rescue medication use/day 2-week mean	X (daily followin	g Screening)	Average of measurements from Day -6 to Day 1(pre-dose) inclusive (at least 4 days must be non-missing)	
SNOT-22 score		Х	Day 1 pre-dose	
PGI-S	Х	Х	Day 1 pre-dose	
Safety				
Blood pressure	X	X	Values from most recent assessment prior to first dose of study treatment which records both systolic and diastolic BP	
Pulse rate	Х	X	Most recent individual value prior to first dose of study treatment	
Clinical Chemistry	Х	Х	Most recent individual value prior to first dose of study treatment	
ECG endpoints	Х	X	Values from most recent ECG conducted prior to first dose of study treatment	
Hematology with differential (including eosinophil count)	X	X	Most recent individual value prior to first dose of study treatment	
Other				
Complement C3 and C4		X	Day 1 pre-dose	
Immunogenicity		Х	Day 1 pre-dose	

Table 3Baseline Definitions & Derivations

NOTES :

- Only records that have been assigned a treatment phase of 'pre-treatment' will be considered as baseline assessments.
- ADSD is to be completed before going to bed and refers to asthma symptoms during the day. Day 1

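### At the Week 26 dosing visit, the QTcF change stopping criterion compares a machine read with a central over-read baseline, and the schedule note does not match Section 7.1.2 on which Visit 2 read applies

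*Protocol*

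**What the plan says.** **Protocol 7.1.2 (QTc Stopping Criteria).** One of the criteria is "Change from baseline of QTcF >60 msec". On the baseline: "The QTcF value from the 12-lead ECG central over-read at randomisation Visit 2 should be used as baseline QTcF value". The scope is general: "for any changes from baseline calculations during the study". The next sentence has the stopping criteria assessed after randomisation on central over-reads, "with the exception of Visit 10 (Week 26) where 12-lead ECG machine read values should be used".

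**Protocol 1.3 (Schedule of Activities, 12-lead ECG note), repeated in Appendix 11, Table 6.** ECGs are to be done and assessed before dosing. Over-reads are the values to use at all visits "with the exception of Visit 2 and Visit 10 where 12-lead ECG machine read values should be used". The note does not say for which purpose.

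**Protocol 5.3.2 (Randomisation Exclusion Criteria).** Participants above the QTcF limits "in the 12-lead ECG machine read at randomisation Visit 2 are excluded".

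**Protocol 6.4.1.** Study intervention is given at Visit 2 (Week 0) and Visit 10 (Week 26) only.

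**SAP 4.1.2, Table 3.** The baseline for ECG endpoints is "Values from most recent ECG conducted prior to first dose of study treatment". No reading method is named.

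**SAP 4.6.3.3.** QTcF change is summarised at Weeks 2, 26, 28 and 52, and each participant's maximum change is put into categories with breaks at 30 and 60 msec. No reading method is named here either.

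**The concern.** A change score is interpretable when both values are measured in the same way. If the machine algorithm and the central reader differ systematically on the same tracing, subtracting one from the other puts that difference straight into the change. Under Section 7.1.2 this happens at Visit 10, the one visit after randomisation at which a participant either receives or does not receive a further dose. An individual could cross, or fail to cross, the 60 msec line because the reading method changed.

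The schedule note adds to the uncertainty. A site following it literally would take the machine read as the Visit 2 value, whereas Section 7.1.2 takes the over-read as baseline.

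The SAP does not settle the matter for reporting. QTc prolongation is an adverse event of special interest, and SAP 4.6.2.1 removes it from the other special-interest tables and reports it only through the ECG section. The reading method behind those ECG tables therefore needs to be known.

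**Working it through.** The plan states no figure that could be reproduced. The check sets the passages side by side and then illustrates the arithmetic.

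**Step 1. Which reads enter each QTcF change?**

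| Visit | Under Section 7.1.2 | If the schedule note also governed baseline |
|---|---|---|
| Week 2 | over-read minus over-read | over-read minus machine |
| Week 26 (Visit 10) | machine minus over-read | machine minus machine |
| Week 28 | over-read minus over-read | over-read minus machine |
| Week 52 | over-read minus over-read | over-read minus machine |

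Neither literal reading gives matched values at every visit. Section 7.1.2 is the passage that defines baseline, so the left-hand column is the stated rule for the change criterion.

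**Step 2. Which criteria are exposed?** QTcF above 500 msec and uncorrected QT above 600 msec involve no subtraction, so the mismatch does not arise for them. The exposure is the change criterion at Visit 10.

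**Step 3. Effect of a systematic offset.** Let b be the machine read minus the over-read of the same ECG. The documents do not give b, so every value here is an assumption. The Visit 10 change equals the same-read change plus b, so a mixed-read change above 60 msec corresponds to a same-read change above 60 - b:

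- b = +5 gives 60 - 5 = 55 msec; b = +10 gives 50 msec.
- b = -5 gives 60 + 5 = 65 msec; b = -10 gives 70 msec.
- b = 0 leaves 60 msec.

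**Step 4. Effect of random disagreement between reads.** Assume that the same-read change is normal with mean 0 and SD 20 msec, and that the read difference is independent with mean b and SD s. The chance of exceeding the limit is 1 - Φ((60 - b)/√(20² + s²)).

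| b (msec) | s = 0 | s = 10 | s = 15 |
|---|---|---|---|
| -10 | 0.023% | 0.087% | 0.256% |
| 0 | 0.135% | 0.365% | 0.820% |
| +10 | 0.621% | 1.267% | 2.275% |

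For b = 0 and s = 15: √(400 + 225) = 25, 60/25 = 2.4, and the upper tail is 0.82%.

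To put this in people, take all 375 planned participants, an upper limit for attendance at Visit 10. With no read difference the expected number is 375 × 0.00135 = 0.5. With b = +10 and s = 10 it is 375 × 0.01267 = 4.8. With b = -10 and s = 10 it is 375 × 0.00087 = 0.3. These figures show scale only; they are not predictions.

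**The case against.** **The schedule note can be reconciled by purpose.** It opens by requiring pre-dose assessment and then excepts exactly the two dosing visits. Section 5.3.2 uses the Visit 2 machine read for same-day eligibility, and Section 7.1.2 gives the over-read the separate task of serving as baseline. A reader might infer that the passages contradict each other irreconcilably. They do not: the note never mentions baseline, and the likely intent can be worked out. What remains is that the note is unqualified and a site has to infer the distinction. This argument does not touch the mixed subtraction at Visit 10, which Section 7.1.2 itself prescribes.

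**A machine read at a dosing visit is understandable.** A decision is needed that day. This stands: the point is the unmatched baseline, not the use of a machine read.

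**The Week 26 safety summaries are not shown to be affected.** A reader might infer that every Week 26 mean change in the report is shifted. The documents do not support that. The Visit 10 exception in Section 7.1.2 concerns the assessment of stopping criteria, not tabulation. The SAP names no read, and its Introduction leaves data handling conventions and display details to a separate programming specification. The tables could use matched reads throughout.

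**Between-arm bias is not shown.** An offset common to both arms would cancel from the difference in mean change. It would not cancel from within-arm means, threshold counts or an individual stopping decision.

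**Other safeguards.** Section 8.3.3 requires two further ECGs when the QT is prolonged, and the average of the three decides discontinuation. That reduces random error but leaves a systematic offset in place. Section 2.3.1 reports that no first-in-human participant met the QTcF criteria requiring additional monitoring, so few participants may come near the limit. Both considerations reduce the likely number affected. Neither makes the two reads comparable.

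**Conclusion.** The point holds in a limited form. By the stated rule in Section 7.1.2, the change-from-baseline criterion at the second-dose visit compares two reading methods. The schedule note does not match that section on the Visit 2 value unless its purpose is inferred from Section 5.3.2.

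The reach is one criterion at one visit. Size and direction are unknown. The range of 50 to 70 msec for the effective limit rests wholly on the assumed offset of ±10 msec, and the exceedance probabilities rest also on assumed normality and standard deviations. For the SAP, the supported conclusion is that the reading method is not stated, so the Week 26 summaries and maximum-change categories may or may not carry the mix.

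This is worth correcting because it bears on an individual stopping decision. It does not threaten the efficacy conclusions.

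**What to change.** **Protocol.** Reconcile the ECG note in Section 1.3, its copy in Appendix 11 Table 6, Section 5.3.2 and Section 7.1.2. For each use (randomisation eligibility, baseline, absolute stopping criteria, and the change-from-baseline criterion at Visit 10), state which read applies at Visit 2 and at Visit 10. No view is taken here on which read or which stopping rule is clinically right.

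**SAP.** In Table 3 and Section 4.6.3.3, name one reading method for both the baseline and the post-baseline values in the QTcF change summaries, including the maximum-change categories.

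**Cost.** Wording in both documents. The protocol already provides for a machine read and a central over-read at Visit 2, so no additional ECG is needed.
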